3.5 Exploratory Endpoints

The exploratory endpoints are as follows:

- Change in frequency of hot flashes from predose (Day -1) as assessed by skin conductance
- Change from baseline in frequency of moderate to severe hot flashes, hot flash average severity, and hot flash severity score, as measured by twice daily diary throughout the study
- Change from baseline in frequency of hot flashes as measured by continuous day time diary from Day -1 predose to Day 7 and to Day 14
- Change from baseline in night time awakenings (NTA) secondary to hot flashes as measured by twice daily diary
- Change in luteinizing hormone (LH) AUC₀₋₈ hours on Day-1 versus Day 1 and Day 7

- To explore the relationship between plasma concentrations and placebo-corrected, change from baseline QTcF and QTcB values using concentration effect modeling, depending on the results observed.

4 STUDY DESIGN

4.1 General

This is a multicenter, double-blind, randomized, placebo-controlled multiple ascending dose trial in postmenopausal women with vasomotor symptoms.

Subjects will be recruited into a maximum of 5 sequentially-dosed cohorts; Cohort 1 (50 mg NT-814), Cohort 2 (100 mg NT-814), Cohort 3 (150 mg NT-814), and, if needed, 2 further cohorts up to 400mg NT-814. Refer to [Figure 1](#) for the study design schematic.

For each cohort, subjects will enter a 4 week screening period to determine eligibility. Twenty eligible subjects will be randomized per cohort (15 active and 5 placebo).

During screening, each subject will be required to complete twice-daily diaries. Eligible subjects will demonstrate, at the baseline visit, an average 24-hour moderate to severe hot flash frequency of ≥ 7 and ≤ 20 , based upon the average daily frequency of all available readings (at least 4 days) in the final week of screening (Week -1). If, at the baseline visit, subjects have an average 24-hour hot flash frequency < 7 /day or > 20 /day, they will be discontinued from the study. In addition, subjects who have a change of $\geq 50\%$ in average 24-hour hot flash frequency between the first and second week of screening (i.e., Week -2 and Week -1) will also be discontinued. Subjects will also be provided with the continuous daily diary during screening and instructed to start completing this on the morning of Day -1 after waking, prior to admission to the clinic, and to continue to complete this throughout Day -1.

It may be necessary to extend a patient's screening period beyond 28 days (with the approval of the sponsor) when a subject is held over from one cohort to the next because the original cohort into which they would have been enrolled is complete. If this occurs, the following safety procedures must be repeated such that the most recent evaluation occurs within 28 days of the rescheduled randomization:

- Biochemistry and hematology
- Vital signs
- 12-lead ECG
- Physical examination

If the subject has completed (or partially completed) the screening twice daily Hot Flash Diary this must still be repeated and a new diary started on the new planned Day -15 and completed for the 2 weeks up to Day -2. Eligibility will be assessed on the repeated diary, not the initial one. If the subject had not started completing their screening diary at the time screening was put on hold, they will start this screening diary on the re-scheduled Day -15.

Eligible subjects will be admitted to the Clinical Pharmacology Units (CPUs) as inpatients on the morning of Day -1 and will be fitted with and instructed on use of a sternal skin conductance monitor and Holter monitor, which will be worn continuously until discharge from the clinic on Day 8. Both the Holter monitor and sternal skin conductance monitor will be refitted on return to the CPU on Day 14. Routine safety monitoring will be carried out to form the baseline for comparisons for the remainder of the study.

On Day 1, the subjects will be randomized in a 3:1 ratio to once daily (QD) morning doses of NT-814 or placebo, to be taken for a total of 14 days. Subjects will be monitored as inpatients from Day -1 to Day 8, and will undergo blood draws for intensive PK sampling, safety monitoring, blood hormonal profiling, 24-hour skin conductance measurements, and continuous completion of hot flash diaries.

Subjects will be discharged from the clinic on Day 8 without any monitoring devices, providing there are no safety concerns and will undergo dosing for a further 5 days as an outpatient. Subjects will be instructed to continue recording details of the hot flashes experienced, using the twice daily diary. They will be provided with the continuous daily diary and instructed to start completing this upon waking on the morning of Day 14 prior to admission to the clinic. They will be re-admitted to clinic on the morning of Day 14 for the final dose and undergo the same assessments with the same devices, including Holter and skin conductance, as Day 1. Subjects will be discharged following the 24-hour post Day 14 assessments (Day 15). Subjects will return to the clinic, as outpatients, for a single PK sample on the mornings of Days 16 and 17 (48 hours and 72 hours after the Day 14 dose respectively).

Throughout the study, subject safety will be closely monitored for safety including assessments of AEs, 12-lead ECGs, arterial oxygen saturation using pulse oximetry, vital signs (sitting and standing BP, HR, oral body temperature, and respiration rate), clinical labs and physical examinations.

[figure not shown]
At the end of each cohort, a blinded review of PK and safety data from all subjects will be conducted by the Safety Review Committee to confirm it is safe to proceed to the next dose. This review must comprise complete data up to Day 17 from a minimum of 14 subjects per cohort.

In the case of any safety concern or ambiguous data from any one of the cohorts, either individual subjects or the entire cohort may be unblinded to enable decision making. If this happens, a separate unblinded Safety Review Committee will be used to maintain the integrity of following cohorts if needed.

Subjects may not participate in more than one cohort.

A final follow-up visit will be conducted by phone one week after completion of dosing for each cohort, unless a CPU visit is deemed more appropriate by the Investigator to follow-up on any ongoing AEs.

Figure 1 Study Schematic

4.2 Study Population

The study population will include postmenopausal female subjects, 40 to 65 years of age. Subjects will have an average of ≥ 7 and ≤ 20 moderate to severe hot flashes/day during the last week's twice daily diary during screening and have a change of $< 50\%$ in average 24-hour hot flash frequency between the first and second week of screening period twice daily diary (Week -2 and Week -1).

4.3 Evaluations at Screening and Check-in

4.3.1 Screening

Screening procedures (Day -28 to Day -1) will include the following:

- Informed consent
- Medical history and concomitant disease evaluation
- Physical examination
- Evaluation of study entry criteria
- Vital signs (sitting and standing BP, HR, oral body temperature, arterial oxygen saturation, respiration rate)

- Body weight
- 12-lead ECG
- Hot flash twice daily diary: Subjects will complete the twice daily diary for the 2 weeks prior to the baseline visit to ascertain eligibility. Subjects will record NTAs. The diary will be provided to subjects during screening.
- Recording of AEs and serious adverse events (SAEs)
- Clinical laboratory sampling (for chemistry and hematology)

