8.10 Analysis of Efficacy Data

All efficacy analyses will be performed using the Full Analysis Set and are considered as exploratory. Any statistical hypothesis tests and/or CIs will be two-sided, using a type I error rate of 0.1. No adjustments will be made for multiplicity in this early phase study. An unstructured covariance matrix is planned for the analyses that use linear mixed-effects models. However, alternative covariance matrices may be used if the unstructured matrix causes model convergence issues.

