8.10.1 Twice Daily Hot Flash Paper Diaries

8.10.1.1 Frequency of Hot Flashes

Frequency by day

Daily (24-hour) frequency of hot flashes for Day Y will be equal to the number of hot flashes recorded on Day Y (day time hot flushes recorded in the evening + night time hot flushes recorded the following morning).

The daily frequency of mild, moderate, severe, moderate/severe, and total hot flashes will be summarized for each day. The mean (\pm SE) frequency of mild, moderate, severe, moderate/severe (moderate and severe combined), and total hot flashes will be displayed graphically by day (Day -8 onwards).

Average daily frequency by week

The average daily frequency of hot flashes for each of Week -1, Week 1, and Week 2 will be equal to the average of the daily frequency of hot flashes from Day -8 to Day -2 inclusive, from Day 1 to Day 7 inclusive, and from Day 8 to Day 14 inclusive, respectively.

The average daily frequency by week and the change from Week -1 (for Week 1 and Week 2) of mild, moderate, severe, moderate/severe, and total hot flashes will be summarized descriptively by treatment.

Statistical analysis

The analysis will test the treatment difference of change in the average daily frequency of moderate/severe hot flashes from Week -1 to each of Week 1 and Week 2.

The analysis will be based on a linear mixed-effects model with the change from Week -1 as a dependent variable, treatment, week, treatment-by-week interaction as fixed effects, subject as a random effect, and baseline (frequency of moderate/severe hot flashes at Week -1) and baseline-by-week interaction as covariates. Subjects dosed with placebo will be analyzed as a pooled group. An unstructured covariance matrix will be specified for the repeated measures at postdose timepoints for each subject. From this analysis, the least-squares (LS) mean and 2-sided 90% CIs will be calculated for the contrast “NT-814 versus placebo” for each treatment and each postdose week, separately.

Following is the SAS code for reference:

```
proc mixed data=dataset ;  
class TRT <50 mg NT-814, 100 mg NT-814, 150 mg NT-814, etc... , placebo> WEEK <1,2> USUBJID;  
model CHG = TRT WEEK TRT*WEEK BSL BSL*WEEK / s ddfm=kr;  
random USUBJID;  
repeated WEEK / type=un subject=USUBJID;  
lsmeans TRT*WEEK / cl diff alpha=0.1;  
run;
```

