3. STUDY DESIGN

This is a multi-center, double-blind, randomized, placebo-controlled multiple ascending dose trial in post-menopausal women with vasomotor symptoms. Subjects will be recruited into sequentially dosed cohorts; Cohort 1 (50 mg NT-814 or placebo), Cohort 2 (100 mg NT-814 or placebo), Cohort 3 (150 mg NT-814 or placebo) and Cohort 4 (300 mg NT-814 or placebo). For each cohort, subjects will enter a 4-week screening period to determine eligibility. Twenty eligible subjects will be randomized per cohort (15 active and 5 placebo).

On Day 1, the subjects will be randomized in a 3:1 ratio to once daily (morning) doses of NT-814 or placebo, to be taken for a total of 14 days. Subjects will be monitored as an inpatient from Day -1 to Day 8 and will undergo blood draws for intensive PK sampling, safety monitoring and for impact on blood hormonal profiling as well as 24-hour skin conductance measurements and continuous completion of hot flash diaries.

Subjects will be discharged from the clinic on Day 8 without any monitoring devices, providing there are no safety concerns and will undergo dosing for a further 5 days as an outpatient. Subjects will be instructed to continue recording details of the hot flashes experienced, using the twice daily diary. They will be provided with the continuous daily diary and instructed to start completing this upon waking on the morning of Day 14 prior to admission to the clinic. They will be re-admitted to clinic on the morning of Day 14 for the final dose and undergo the same assessments with the same devices including Holter and skin conductance as Day 1. Subjects will be discharged following the 24-hour post Day 14 assessments (Day 15). Subjects will return to the clinic, as outpatients, for a single PK sample on the mornings of Days 16 and 17 (48 hours and 72 hours after the Day 14 dose respectively).

Throughout the study, subjects will be closely monitored for safety including assessments of AEs, 12-lead ECGs, arterial oxygen saturation using pulse oximetry, vital signs (sitting and standing BP, heart rate, oral body temperature, and respiration rate), clinical labs and physical examinations.

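### The twice-daily diary models adjust for Week -1 only, although a Week -2 average is also collected before randomization and could sharpen these exploratory comparisons at little cost

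*SAP*

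**What the plan says.** **Collection.** SAP 4.3.1 states: "Subjects will complete the twice daily diary for the 2 weeks prior to the baseline visit to ascertain eligibility". For women held over between cohorts, SAP 4.1 gives the days: "a new diary started on the new planned Day -15 and completed for the 2 weeks up to Day -2". That is 14 days. SAP 8.10.1.1 defines Week -1 as Day -8 to Day -2, which leaves Day -15 to Day -9 as Week -2.

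**Use of Week -2.** SAP 4.1 discontinues a woman with a change of 50% or more "in average 24-hour hot flash frequency between the first and second week of screening". SAP 4.2 and protocol 7.2 carry the same rule. Applying it requires a Week -2 average for each woman.

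**Model.** In SAP 8.10.1.1 the dependent variable is change from Week -1. The only baseline terms are "baseline (frequency of moderate/severe hot flashes at Week -1) and baseline-by-week interaction as covariates". The reference code agrees: CHG = TRT WEEK TRT*WEEK BSL BSL*WEEK. Sections 8.10.1.2 to 8.10.1.4 apply the same analysis to average severity, severity score and both night-time-awakening endpoints. No weekly Week -2 score is defined for analysis.

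**Comparison.** Each cohort has 15 active and 5 placebo women, and "Subjects dosed with placebo will be analyzed as a pooled group". Placebo therefore numbers 20 with four cohorts (as in section 3 of the PK SAP) or 25 with five. SAP 8.10 calls all efficacy analyses exploratory and adds: "Any statistical hypothesis tests and/or CIs will be two-sided, using a type I error rate of 0.1".

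**The concern.** The models deliver a 90% interval for each dose against placebo at each week. With about 15 women against 20 to 25, the width of those intervals limits what can be learned about dose and hot flashes, which is a stated exploratory objective.

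Week -1 is one noisy weekly average of a woman's usual frequency. It is also the week on which she must average between 7 and 20 moderate to severe flashes per day, so its range is cut at both ends. Week -2 is a second pre-randomization measurement of the same quantity. If it predicts the post-dose weeks beyond what Week -1 already predicts, leaving it out gives up precision that needs no new data. At stake is the width of the exploratory intervals and nothing else.

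**Working it through.** **No figure in the plan to reproduce.** The documents give no SD, correlation, power or interval width for any diary endpoint. The only power statement (SAP 8.12) concerns AUC0-24 and does not bear on this point.

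**Inputs from the documents.** 15 women per dose, 20 or 25 pooled placebo, two-sided 90% intervals, and the entry rules (Week -1 average 7 to 20, change below 50%).

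**Assumptions.** Let r be the correlation between adjacent weeks and s the correlation between Week -2 and Week 1. Neither is in the documents.

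**Formula.** With Week -1 alone, the residual variance of Week 1, as a fraction of its total variance, is 1 - r². Adding Week -2 multiplies this by

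1 - [(s - r²)/(1 - r²)]²

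The interval width is multiplied by the square root. Three structures:

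- Equal correlation, s = r: the factor is 1 - [r/(1 + r)]². At r = 0.7 this is 1 - 0.412² = 0.830, width 0.911.
- Halfway decay, s = (r + r²)/2: the factor is 1 - [r/(2(1 + r))]². At r = 0.7 this is 1 - 0.206² = 0.958, width 0.979.
- Pure AR(1), s = r²: the factor is 1, so there is no gain.

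**Effect of the entry rules.** A simulation applied both entry rules to weekly values with an assumed mean of 10 and SD of 4 before selection, and with no drug effect. Half-widths are in flashes per day for 15 against 20 women.

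| r | Width ratio, equal correlation, no selection | Same, after entry rules | Half-width, after entry rules | Width ratio, halfway decay, no selection | Width ratio, pure AR(1) |
|---|---|---|---|---|---|
| 0.5 | 0.943 | 0.966 | 1.92 to 1.85 | not computed | 1.000 |
| 0.6 | 0.927 | 0.953 | 1.77 to 1.69 | 0.982 | 1.000 |
| 0.7 | 0.911 | 0.937 | 1.58 to 1.48 | 0.979 | 1.000 |
| 0.8 | 0.896 | 0.917 | 1.33 to 1.22 | 0.975 | 1.000 |
| 0.9 | 0.881 | 0.891 | 0.98 to 0.87 | 0.972 | 1.000 |

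So Week 1 intervals are 3% to 11% narrower under equal correlation after selection, 2% to 3% narrower under halfway decay, and unchanged under pure AR(1). Charging for the extra degree of freedom (80 women, five groups, 74 to 73) moves the unselected equal-correlation ratios only from 0.943–0.881 to 0.949–0.887.

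**Second simulation.** Poisson-lognormal weekly counts under the same entry rules, with AR(1) parameter 0 to 0.6, gave Week 1 variance ratios of 0.80 to 0.98 over 18 settings. Square roots are 0.894 and 0.990, so intervals were about 1% to 11% narrower.

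**Not covered.** The first simulation returned the same ratios for Week 2 as for Week 1, but that follows from the equal-correlation and AR(1) assumptions and is not a separate estimate. Halfway decay was not worked for Week 2, and nothing was computed for severity or night-time awakenings.

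**Cost of losing women.** If a missing covariate removed one woman from each side, the contrast variance would change by (1/14 + 1/19)/(1/15 + 1/20) = 0.1241/0.1167 = 1.063, a rise of about 6%.

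**The case against.** The strongest reply is that adjusting for the last pre-dose week is a valid, coherent, pre-specified analysis, and that any trial with spare baseline data could add a covariate. The efficacy endpoints are exploratory, protocol 11.3.4 calls their analysis mainly descriptive, and the sample size rests on PK exposure. That stands as to weight: the plan contains no error here. It does not remove the point, because the measurement is already taken and using it leaves the contrast unchanged.

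Other parts also stand:

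- **Size.** A reader might infer that the intervals are certainly wider than they need be. The documents do not support that, since the gain depends on a correlation structure they do not give and is nil under pure AR(1). Pure AR(1) is unlikely for averages of four to seven noisy daily counts, but a gain of only 2% to 3% is plausible. Varied response to active drug would reduce it further.
- **Bias.** A reader might infer bias from selecting on Week -1. Selection precedes randomization and applies to all arms alike, so it does not bias the contrast. Week -2 is itself restricted through the 50% rule.
- **Discarding.** A reader might infer that Week -2 is thrown away. Only the graphs are limited to Day -8 onwards. The daily summaries in SAP 8.10.1.1 do not expressly exclude Week -2, and the diary data are listed.
- **Missing data.** The four-day minimum for eligibility in SAP 4.1 is stated only for Week -1. SAP 8.2 requires four complete days for a weekly value and does not impute efficacy endpoints. Without a rule for incomplete Week -2 data, PROC MIXED would drop women with a missing covariate, and the 6% loss shown above could cancel a small gain.

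**Conclusion.** The point holds as a modest, conditional improvement. The twice-daily diary models omit a pre-randomization measurement that the trial already collects. The consequence is a possible loss of precision in exploratory endpoints, without bias and without any effect on the primary PK and safety objective.

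For Week 1 frequency, the avoidable width lies between about 0% (pure AR(1)) and 11% (equal correlation up to 0.9, after the entry rules). This rests on assumed correlations, an assumed weekly mean and SD, and no drug effect in the simulation. The range should not be carried over to Week 2, severity or night-time awakenings, nor to the continuous diary and skin-conductance models, which use Day -1 as baseline.

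**What to change.** Amend SAP 8.10.1.1, and through it 8.10.1.2 to 8.10.1.4, before unblinding:

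1. Keep change from Week -1 as the dependent variable and keep Week -1 with its interaction with week.
2. For each endpoint, define BSL2 as that endpoint's Week -2 average (Day -15 to Day -9), and fit `model CHG = TRT WEEK TRT*WEEK BSL BSL*WEEK BSL2 BSL2*WEEK`.
3. Compute BSL2 from all available complete days, as a stated exception to the four-day rule in SAP 8.2. If a woman has none, use one treatment-blind value, the mean over all women. This fills a pre-dose covariate and imputes no outcome, and it keeps every woman in the model.

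The treatment contrast and its meaning do not change. The cost is about two degrees of freedom among 80 to 100 women and a short covariate definition. The downside is little or no gain if the correlation between weeks decays quickly.

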4.3.2 Check-in

Check-in procedures (Day -1) will include the following:

- Medical history and concomitant disease evaluation
- Evaluation of study entry criteria
- Vital signs (sitting and standing BP, HR, oral body temperature, arterial oxygen saturation, respiration rate)
- Body weight
- 12-lead ECG
- Hot flash twice daily diary and day time continuous hot flash paper diary: Subjects will record the occurrence and severity of the flash (scale 1 to 3) in a continuous diary. Subjects will be instructed to start completing it after waking on the morning of Day -1 prior to admission and throughout the day and night.
- Sternal skin conductance monitor fitting
- Holter monitor fitting
- Recording of AEs and SAEs
- Clinical laboratory sampling (for chemistry and hematology) and urinalysis
- Sampling for LH, estradiol, testosterone, FSH, ACTH, cortisol, TSH, T3, and T4

4.4 Randomization and Treatment Assignments

Following screening and confirmation of eligibility, subjects in each cohort will be randomized on Day 1 in a 3:1 ratio to receive either NT-814 or placebo. The investigational medicinal

product (IMP) that each subject will receive will be allocated by an Interactive Web Response Services tool provided by the Clinical Research Organization on behalf of the Sponsor.

4.5 Study Drug Administration

Subjects will be administered study medication in the morning, according to the randomization schedule, at the CPU on Day 1 through Day 8. On Day 8, subjects will be dispensed study medication to be self-administered on Days 9 to 13 (1-2 days' overage should be included). On Day 14, subjects will be administered study medication on the morning of admission to the CPU. Subjects will be reminded to take the study medication at the same time each morning and to return any unused medication when they return to CPU on Day 14. Subjects will be required to fast overnight prior to study drug administration on Day 1 through Day 14.

4.6 Concomitant Medications

All concomitant medications taken during the study will be recorded in the electronic case report form (eCRF) with indication, dose information, and dates of administration. Subjects using the following medications will be excluded from the study:

- Any antidepressants (e.g., selective serotonin reuptake inhibitor, serotonin-norepinephrine reuptake inhibitor) within 4 weeks of screening
- Neurokinin receptor antagonists within 2 weeks of screening
- Women on tamoxifen (or other estrogen modulating drugs) or receiving chemotherapy/radiation therapy within 4 weeks of screening or planned antineoplastic chemotherapy/radiation therapy
- Drugs or herbal medications that could be associated with hot flash-like symptoms including nicotinic acid, calcium channel blockers, clonidine, opioid drugs, and black cohosh within 2 weeks of screening
- Drugs that are highly protein bound (e.g., warfarin and digoxin) within 4 weeks of screening visit, use of non-steroidal anti-inflammatory drugs from the time of signing informed consent
- Use of non-steroidal anti-inflammatory drugs from the time of signing the informed consent
- Use of any of the following hormonal treatments within the washout period stated before screening:
 - Within 1 week for prior vaginal hormonal products (e.g., rings, creams, gels)

- Within 4 weeks for prior transdermal estrogen alone or estrogen/progestin products
- Within 12 weeks for prior oral estrogen and/or progestin therapy
- Within 3 months for prior progestin implants and estrogen alone injectable drug therapy
- Within 6 months for prior estrogen pellet therapy or progestin injectable drug therapy
- Subjects using the following medications within 2 weeks prior to first dosing (or within 5 times the half-life of that medication, whichever is longer) will be excluded from the study:
 - Inhibitors of cytochrome P450 (CYP) 3A4 (including but not limited to macrolide antibiotics, human immunodeficiency virus protease inhibitors, azole antifungal drugs, cyclosporine, calcium channel inhibitors, and cimetidine)
 - Inducers of CYP3A4 (including but not limited to rifampicin, carbamazepine, efavirenz, bosentan, modafinil, and St. John's wort)
 - Known P-glycoprotein inhibitors (including but not limited to amiodarone, azithromycin, carvedilol, clarithromycin, conivaptan, cyclosporine, diltiazem, dronedarone, erythromycin, felodipine, itraconazole, ketoconazole, lopinavir, ritonavir, quinidine, ranolazine, and verapamil)
- Known CYP3A4 substrates with a narrow therapeutic range are not allowed from screening until up to 5 times the half-life after the last dose of NT-814 is administered (including but not limited to alfentanil, cyclosporine, dihydroergotamine, ergotamine, fentanyl, pimozone, quinidine, sirolimus, and tacrolimus)

As the inhibition potential of NT-814 with breast cancer resistance protein transporter has not yet been evaluated *in vitro*, an interaction with statins cannot be ruled out. Subjects receiving statins can be allowed into the study, but should be monitored for signs and symptoms of rhabdomyolysis and will be withdrawn from the study if these are observed.

Subjects will be required to inform the study investigator of any regularly taken medications (prescription or over the counter), including hormone replacement therapy, natural and herbal products, vitamins, minerals, or dietary supplements taken within 2 weeks (or less than 5 times the half-life of that medication, whichever is longer) prior to the first dose. Use of such medications should be reviewed with the medical monitor and permitted on a case by case basis.

Subjects must refrain from eating grapefruit, grapefruit juice, Seville oranges, and pomelos within 7 days prior to Day -1 until after their final follow-up visit. Other than this restriction subjects should maintain their usual diet during outpatient periods of the study.

